- j) Assessments during follow up are made every 8-12 weeks, according to investigator's criteria.
- k) A serum or urine pregnancy test will be performed at the Screening Visit, at the Baseline Visit (or within 72 hours prior to the first dose of study medication)
- l) Screening tumor assessments using CT of the chest/abdomen/pelvis and other areas of known disease or newly suspected disease should be performed within 28 days prior to C1D1. Scans of the abdomen, pelvis and other areas of the body may be done with MRI instead of CT, but evaluation of the chest should be done with CT. CT scans should be performed with oral and iodinated IV contrast and MRI scans with IV gadolinium chelate unless there is a medical contraindication to contrast. If iodinated IV contrast is contraindicated, chest CT should be done without IV contrast.
- m) Somatostatin receptor scintigraphy (octreoscan) or PET-CT should be performed and/or available within the previous 6 months before C1D1, only on cohort 1-3. It is not applicable on

Clinical Study Protocol
Drug Substance DURVALUMAB/TREMELIMUMAB
Study Number ESR 15-11561-61-DUNE
EudraCT Nº: 2016-002858-20
Edition Number: 5.0 dated on June 09th, 2021

cohort 4.

- n) Survival data will be collected every 4 weeks until end of treatment phase is declared. All anticancer therapies will be collected. Survival data and other cancer treatments received will be collected every 6 months until close of the study database. The study sponsor may elect to discontinue survival follow-up.
- o) Collection of blood sample to obtain plasma, serum, or other components to be used for biomarker studies. Samples will be obtained at baseline, Cycle 2/Day 1, and at end-of-treatment visit.
- p) All subjects will have collection of most recent archived, tumor-biopsy sections for identification of predictive biomarkers.
- q) Throughout the study from the signature of Informed Consent. SAE irrespective of relationship to study treatment must be reported as soon as possible but not later than one business day. AEs and concomitant meds collected 28 days from last dose.
- r) See section 8.1.3, APPENDIX 2 and APPENDIX 3.
- s) See section 8.1.3, APPENDIX 2 and APPENDIX 3.

LIST OF TABLES

¡Error! Marcador no definido.

LIST OF APPENDICES	23
ABBREVIATIONS AND DEFINITION OF TERMS	24
1. INTRODUCTION	28
1.1 Disease Background	28
1.1.1 Immunotherapies	30
1.1.2 Durvalumab	30
1.1.3 Tremelimumab	31
1.1.4 Durvalumab in combination with tremelimumab	31

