10.3.1 Study recording period and follow-up for adverse events and serious adverse events

Adverse events and serious adverse events will be recorded from time of signature of informed consent, throughout the treatment period and including the follow-up period (90 days after the last dose of durvalumab + tremelimumab).

During the course of the study all AEs and SAEs should be proactively followed up for each subject. Every effort should be made to obtain a resolution for all events, even if the events continue after discontinuation/study completion.

If a subject discontinues from treatment for reasons other than disease progression, and therefore continues to have tumor assessments, drug or procedure-related SAEs must be captured until the patient is considered to have confirmed PD and will have no further tumor assessments.

The investigator is responsible for following all SAEs until resolution, until the subject returns to

Clinical Study Protocol
Drug Substance DURVALUMAB/TREMELIMUMAB
Study Number ESR 15-11561-61-DUNE
EudraCT Nº: 2016-002858-20
Edition Number: 5.0 dated on June 09th, 2021

baseline status, or until the condition has stabilized with the expectation that it will remain chronic, even if this extends beyond study participation.

Follow-up of unresolved adverse events

Any AEs that are unresolved at the subject's last visit in the study are followed up by the investigator for as long as medically indicated, but without further recording in the eCRF. After 90 days, only subjects with ongoing investigational product-related SAEs will continue to be followed for safety.

The sponsor and [REDACTED] retain the right to request additional information for any subject with ongoing AE(s)/SAE(s) at the end of the study, if judged necessary.

Post study events

After the subject has been permanently withdrawn from the study, there is no obligation for the investigator to actively report information on new AE or SAEs occurring in former study subjects after the 90-day safety follow-up period for patients treated with durvalumab + tremelimumab. However, if an investigator learns of any SAEs, including death, at any time after the subject has been permanently withdrawn from study, and he/she considers there is a reasonable possibility that the event is related to study treatment, the investigator should notify the study sponsor, who will inform [REDACTED] Drug Safety.

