10.3.2.1 Reporting of deaths

All deaths that occur during the study, or within the protocol-defined 90-day post-last dose of durvalumab + tremelimumab safety follow-up period must be reported as follows:

- Death that is clearly the result of disease progression should be documented but should not be reported as an SAE.
- Where death is not due (or not clearly due) to progression of the disease under study, the AE causing the death must be reported to as a SAE within **24 hours** (see Section 10.3.2 for further details). The report should contain a comment regarding the co-involvement of progression of disease, if appropriate, and should assign main and contributory causes of death.
- Deaths with an unknown cause should always be reported as a SAE.

Deaths that occur following the protocol-defined 90-day post-last-dose of durvalumab safety follow-up period will be documented as events for survival analysis, but will not be reported as an SAE.

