	Day (±3)	Months (±1 week)						12 Months and every 6 Months (±2 weeks)
		30	2	3	4	6	8	
Physical examination ^a	x	x	x	x	x	x	x	
Vital signs (temperature, respiratory rate, blood, pressure, pulse)	x	x	x	x	x	x	x	
Weight	x	x	x	x	x	x	x	
Urine hCG or serum βhCG	x							
AE/SAE assessment	x	x	x					
Concomitant medications	x	x	x					
Palliative radiotherapy	As clinically indicated							
ECOG performance status	x	x	x		x (and month 9)			x
Subsequent anti/cancer therapy	x	x	x	x	x	x	x	
Survival status: phone contact with subjects who refuse to return for evaluations and agree to be		x	x	x	x	x	x	x (every 2 months)

Clinical Study Protocol
 Drug Substance DURVALUMAB/TREMELIMUMAB
 Study Number ESR 15-11561-61-DUNE
 EudraCT N°: 2016-002858-20
 Edition Number: 5.0 dated on June 09th, 2021

contacted							
Hematology	x	Every 8-12 weeks, according to investigator's criteria					x
Serum chemistry	x	Every 8-12 weeks, according to investigator's criteria					
Thyroid function tests (TSH, and fT3 and fT4) ^b	x	Every 8-12 weeks, according to investigator's criteria					
SPD-L1 concentration (to assess target engagement)		x					
Tumour assessment (CT or MRI)	
For subjects who achieve disease control following 12 months of treatment, tumour assessments should be performed every 12 weeks relative to the date of first infusion thereafter until confirmed PD by RECIST 1.1 by investigational site review. Please refer to SCHEDULE OF STUDY ASSESSMENTS for timings of confirmatory scans.
 
For subjects who discontinue study drug due to toxicity (or symptomatic deterioration), tumour assessments should be performed relative to the date of first infusion as follows: every 12 weeks until confirmed PD by RECIST 1.1 by investigational site review. Please refer to SCHEDULE OF STUDY ASSESSMENTS for timings of confirmatory scans.
 
Upon confirmed PD, scans should be conducted according to local standard clinical practice until a new treatment is started (these scans are optional).
						
^a Full physical exam ^b Free T3 and free T4 will only be measured if TSH is abnormal. They should also be measured if there is clinical suspicion of an adverse event related to the endocrine system. ^c For patient questionnaires different approaches based on indication and study design.							

Appendix 3 Schedule of study procedures: follow-up for subjects who have discontinued durvalumab or tremelimumab treatment due to confirmed progression of disease at the investigator discretion

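### Footnote q of the assessment schedule (protocol and SAP) ends adverse-event and concomitant-medication collection 28 days after the last dose, while protocol section 10.3.1 records adverse events to 90 days

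*Protocol*

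**What the plan says.** **28 days.** In the protocol's schedule of assessments, footnote q to the AEs/SAEs row ends with "AEs and concomitant meds collected 28 days from last dose". The SAP repeats it under Table 1 in section 3.5.1. The sentence before it reads "SAE irrespective of relationship to study treatment must be reported as soon as possible but not later than one business day", and the 28-day sentence itself does not name serious events.

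**90 days.** Protocol section 10.3.1 records AEs and SAEs from consent, "throughout the treatment period and including the follow-up period (90 days after the last dose of durvalumab + tremelimumab"). It lifts the duty to report new events actively only "after the 90-day safety follow-up period for patients treated with durvalumab + tremelimumab". Section 10.3.2.1 covers deaths during the study or "within the protocol-defined 90-day post-last dose of durvalumab + tremelimumab safety follow-up period must be reported as follows".

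**Appendices 2 and 3.** In both follow-up schedules the row "AE/SAE assessment" and the concomitant-medication row carry three marks, which read as day 30, month 2 and month 3 after the last dose. Footnotes r and s of the main schedule send the reader to these appendices.

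**Medications elsewhere.** Section 7.2 asks for concomitant medication up to the final study visit. Section 10.3.1 does not mention medication.

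Neither document says which text takes precedence.

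**The concern.** Safety is a secondary objective in all four cohorts. The synopsis says onset, duration, resolution and concomitant medication will be recorded for toxicities. Two end dates for the same data allow two sites, or a site and the eCRF, to apply different rules while each follows the protocol.

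If the footnote is followed, non-serious events starting on days 29 to 90 go unrecorded, as does the medication given for them. Medication is affected even when the event itself was captured. Appendix 1 describes a steroid taper lasting at least 28 days after improvement, so for an immune-mediated event near the last dose the taper would run past a 28-day medication record. If practice differed between sites, the toxicity tables would combine patients observed for different lengths of time without saying so.

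**Working it through.** No sample-size or power figure is involved. The check is a comparison of texts plus simple arithmetic.

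**1. Size of the gap.** Inputs: 28 days (footnote q) and 90 days (section 10.3.1). 90 − 28 = 62 days, and 62/90 = 0.69 of the post-dose period.

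**2. Gap relative to all recording time from first dose.** With k four-weekly doses, no delays and no retreatment (an assumption), the last dose falls 28(k − 1) days after the first. Recording under section 10.3.1 then runs for 28(k − 1) + 90 days.

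| Doses received | Days from first dose to end of 90-day window | Share lost under footnote |
|---|---|---|
| 1 | 0 + 90 = 90 | 62/90 = 69% |
| 4 | 84 + 90 = 174 | 62/174 = 36% |
| 13 (section 3.1 maximum) | 336 + 90 = 426 | 62/426 = 15% |

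These are shares of time, not of events.

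**3. Appendix visits against day 28.** Day 30 with its ±3-day window spans days 27 to 33, so only a visit on day 27 or 28 falls inside the footnote's limit. Months 2 and 3, each ±1 week, lie wholly outside it. These column positions are read from tables whose headers were displaced in PDF extraction.

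**4. What each text covers on days 29 to 90.**

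| Item | Footnote q | Section 10 | Appendices 2–3 |
|---|---|---|---|
| Non-serious AEs | Not collected | Recorded (10.3.1) | Visits marked |
| SAEs | Reported; 28-day sentence does not name them | Recorded (10.3.1) | Visits marked |
| AESIs, serious or not | Not mentioned | SAE form (10.1.3); no post-dose window given there | Not listed separately |
| Concomitant medication | Not collected | Not addressed | Visits marked |

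The direct conflict lies in the first and last rows.

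**5. The SAP.** Its only explicit AE window is the 28-day footnote. However, SAP 3.4 refers post-treatment assessments to protocol Appendices 2 and 3, and the safety tables set no limit on onset date.

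**6. Which last dose.** Section 10.3.1 counts from the last dose of the two drugs named together. Section 10.3.2.1 does the same, then, for later deaths, counts from the last dose of durvalumab. Under section 5.2.1 tremelimumab stops after up to four doses and durvalumab continues alone for up to nine more. Counted from the last combination dose (day 84 after four doses), 90 days ends on day 174. Counted from the thirteenth durvalumab dose (day 336), it ends on day 426. The two readings differ by 426 − 174 = 252 days for a patient who completes treatment. Section 10.3.1 also requires recording throughout treatment, so the first reading would not stop collection on treatment, but it would leave no defined period after the final durvalumab dose.

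**The case against.** The strongest reply is that a careful site would not stop at day 28. Section 10.3.1 is the dedicated section on recording periods, section 10.3.2.1 calls the 90-day period protocol-defined, and footnotes r and s on the same schedule lead to appendices with later AE visits. Section 8.1.3 does the same. This stands as an argument about likely behaviour. It does not remove the contradiction: footnote q belongs to the AE row and states a limit, and nothing ranks the texts.

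A second reply is that the events that matter most have other routes. Footnote q requires SAE reporting whatever the relationship. For patients who stop for reasons other than progression, section 10.3.1 adds that "drug or procedure-related SAEs must be captured until the patient is considered to have confirmed PD and will have no further tumor assessments". Section 10.1.3 asks for AESIs on the SAE form even when non-serious. This also stands. A reader might infer from the footnote that late immune-related toxicity in general would be lost, and the documents do not support that. What is exposed is non-serious events, including immune-related ones not recognised or reported as AESIs, and concomitant medication.

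A third reply is that the SAP mismatch may be version lag, since the SAP of November 2017 rests on protocol 3.1 and not on edition 5.0. That may explain the SAP copy, but edition 5.0 still carries the 28-day sentence. Nor does the SAP direct anyone to discard events from days 29 to 90, so it cannot be read as truncating the analysis.

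**Conclusion.** This is an internal inconsistency in the current protocol, repeated in the SAP. It concerns a data-collection window and should be corrected. Its size is 62 days: 69% of the post-dose recording period, or about 15% of recording time from first dose for a patient given 13 undelayed doses, and more for early stoppers.

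Two stronger readings are tempting. One is that 69% of post-treatment events would be missed. That needs onset to be uniform over the 90 days, which nothing in the documents supports, and it ignores the SAE and AESI routes. The other is that the reported rates do mix two windows. That requires some sites to have followed the footnote, and the documents do not show what sites or the eCRF did.

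The conclusion rests on the plain wording of footnote q and section 10.3.1. The appendices support it, subject to the reading of their columns noted above.

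**What to change.** 1. Reconcile footnote q in the protocol schedule and in SAP 3.5.1 with the 90-day recording period of section 10.3.1. State the concomitant-medication window explicitly, since section 10.3.1 is silent on it.
2. Define the anchor once, as the last dose of either study drug or the last combination dose, and use it in sections 10.3.1 and 10.3.2.1, footnote q and Appendices 2 and 3. Say how it applies after retreatment (section 5.2.2).
3. Add one sentence to the SAP giving the onset window that the safety tables cover.
4. Confirm what the eCRF and sites collected on days 29 to 90, and describe any variation between sites in the study report.

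The cost is two footnotes, one definition, one SAP sentence and a data-management check. No visits are added, because Appendices 2 and 3 already contain them.

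The fourth step carries most of the practical weight. Section 13.6 places the last subject in at December 2019. Twelve months of treatment plus 90 days runs to about March 2021, before edition 5.0 of June 2021. On that timetable, setting aside delays and retreatment, most post-dose windows had closed by then, so amending the wording alone would recover little.

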APF12	Proportion of patients alive and progression free at 12 months from randomization
AST	Aspartate aminotransferase
AUC	Area under the curve
AUC0-28day	Area under the plasma drug concentration-time curve from time zero to Day 28 post-dose
AUC _{ss}	Area under the plasma drug concentration-time curve at steady state
BoR	Best objective response
BP	Blood pressure
C	Cycle
CD	Cluster of differentiation

Clinical Study Protocol
 Drug Substance DURVALUMAB/TREMELIMUMAB
 Study Number ESR 15-11561-61-DUNE
 EudraCT Nº: 2016-002858-20
 Edition Number: 5.0 dated on June 09th, 2021

CI	Confidence interval
CL	Clearance
C_{max}	Maximum plasma concentration
C_{max,ss}	Maximum plasma concentration at steady state
CR	Complete response
CSA	Clinical study agreement
CSR	Clinical study report
CT	Computed tomography
CTCAE	Common Terminology Criteria for Adverse Event
CTLA-4	Cytotoxic T-lymphocyte-associated antigen 4
C_{trough,ss}	Trough concentration at steady state
CXCL	Chemokine (C-X-C motif) ligand
DoR	Duration of response
EC	Ethics Committee, synonymous to Institutional Review Board and Independent Ethics Committee
ECG	Electrocardiogram
ECOG	Eastern Cooperative Oncology Group
eCRF	Electronic case report form

Clinical Study Protocol
 Drug Substance DURVALUMAB/TREMELIMUMAB
 Study Number ESR 15-11561-61-DUNE
 EudraCT Nº: 2016-002858-20
 Edition Number: 5.0 dated on June 09th, 2021

EdoR	Expected duration of response
EGFR	Epidermal growth factor receptor
EU	European Union
FAS	Full analysis set
FDA	Food and Drug Administration
GCP	Good Clinical Practice
GI	Gastrointestinal
GMP	Good Manufacturing Practice
hCG	Human chorionic gonadotropin
HIV	Human immunodeficiency virus
HR	Hazard Ratio
IB	Investigator's Brochure
ICF	Informed consent form
ICH	International Conference on Harmonisation
IDMC	Independent Data Monitoring Committee
IFN	Interferon
IgE	Immunoglobulin E

Clinical Study Protocol
 Drug Substance DURVALUMAB/TREMELIMUMAB
 Study Number ESR 15-11561-61-DUNE
 EudraCT Nº: 2016-002858-20
 Edition Number: 5.0 dated on June 09th, 2021

IgG	Immunoglobulin G
IHC	Immunohistochemistry
IL	Interleukin
ILS	Interstitial lung disease
IM	Intramuscular
IMT	Immunomodulatory therapy
IP	Investigational product
irAE	Immune-related adverse event
IRB	Institutional Review Board
irRECIST	Immune-related Response Evaluation Criteria in Solid Tumors
ITT	Intent-to-Treat
IV	Intravenous
IVRS	Interactive Voice Response System
IWRS	Interactive Web Response System
mAb	Monoclonal antibody
MDSC	Myeloid-derived suppressor cell
MedDRA	Medical Dictionary for Regulatory Activities

Clinical Study Protocol
 Drug Substance DURVALUMAB/TREMELIMUMAB
 Study Number ESR 15-11561-61-DUNE
 EudraCT Nº: 2016-002858-20
 Edition Number: 5.0 dated on June 09th, 2021

MHLW	Minister of Health, Labor, and Welfare
miRNA	Micro-ribonucleic acid
MRI	Magnetic resonance imaging
NCI	National Cancer Institute
NE	Not evaluable
NSCLC	Non-small-cell lung cancer
OAE	Other significant adverse event
ORR	Objective response rate
OS	Overall survival
PBMC	Peripheral blood mononuclear cell
PD	Progressive disease
PD-1	Programmed cell death 1
PD-L1	Programmed cell death ligand 1
PD-L2	Programmed cell death ligand 2
PDx	Pharmacodynamic(s)
PFS	Progression-free survival
PFS2	Time to second progression

Clinical Study Protocol
 Drug Substance DURVALUMAB/TREMELIMUMAB
 Study Number ESR 15-11561-61-DUNE
 EudraCT Nº: 2016-002858-20
 Edition Number: 5.0 dated on June 09th, 2021

PGx	Pharmacogenetic research
PK	Pharmacokinetic(s)
PR	Partial response
q2w	Every 2 weeks
q3w	Every 3 weeks
q4w	Every 4 weeks
q6w	Every 6 weeks
q8w	Every 8 weeks
QTcF	QT interval corrected for heart rate using Fridericia's formula
RECIST 1.1	Response Evaluation Criteria in Solid Tumors, version 1.1
RNA	Ribonucleic acid
RR	Response rate
RT-QPCR	Reverse transcription quantitative polymerase chain reaction
SAE	Serious adverse event
SAP	Statistical analysis plan
SAS	Safety analysis set
SD	Stable disease

Clinical Study Protocol
 Drug Substance DURVALUMAB/TREMELIMUMAB
 Study Number ESR 15-11561-61-DUNE
 EudraCT Nº: 2016-002858-20
 Edition Number: 5.0 dated on June 09th, 2021

SNP	Single nucleotide polymorphism
SoC	Standard of Care
sPD-L1	Soluble programmed cell death ligand 1
T₃	Triiodothyronine
T₄	Thyroxine
TSH	Thyroid-stimulating hormone
ULN	Upper limit of normal
US	United States

1. INTRODUCTION

Neuroendocrine neoplasms constitute a heterogeneous group of tumors derived from the Kultchitzky cells of the diffuse neuroendocrine system located in the gastrointestinal tract (origin of classical carcinoid tumors), pancreatic islet cells (origin of pancreatic endocrine tumors) and lung (origin of typical and atypical carcinoids). Advanced disease is common at diagnosis leading to limited options of curative strategies, so general prognosis is poor. Neuroendocrine neoplasms are considered rare diseases, however, taken all together into account and the natural history of well-differentiated tumors, their prevalence is increasing. Systemic treatment options have been limited for several years. However, in the last decade, the better knowledge of molecular biology of neuroendocrine neoplasms has increased the interest to develop targeted agents in this field, changing the scenario of possible therapies for advanced disease. Even though, treatment options are still limited.

Immune balance has always been related with neuroendocrine neoplasms. Prolonged stabilizations have often been described without treatment and initial immune modulators, such as interferon, have demonstrated antitumoral effects in these tumors. Recent advances in immunotherapy have permitted the development of new targeted agents with higher efficacy and lower toxicity that opens a new treatment option for patients with advanced neuroendocrine tumors.

1.1 Disease Background

Well-differentiated gastroenteropancreatic and lung neuroendocrine tumors are generally malignancies with a prolonged natural history. However, clinical behavior is heterogeneous and when tumor progression is observed, treatment options are limited. Although advanced neuroendocrine neoplasms represent less than 2% of all gastrointestinal cancers, they constitute the second most prevalent advanced tumor of the gastrointestinal tract after colorectal cancer (Yao et al, 2008). The biological behavior of neuroendocrine neoplasms depends mainly on their histological characteristics, defined by the differentiation grade and Ki67 expression. The most recent 2010 WHO classification divides neuroendocrine neoplasms in three groups regarding Ki67 value and mitotic count: neuroendocrine tumors that include grade 1 (G1) and grade 2 (G2) with Ki67 value $\leq 20\%$ and mitotic count ≤ 20 mitoses x 10 HPF, and neuroendocrine carcinomas that include grade 3 (G3) with Ki67 $> 20\%$ and/or mitotic count > 20 mitoses x 10 HPF.

Table 1. Groups of neuroendocrine neoplasms following the WHO classification

Grade	Lung and Thymus	GEP-NETs	
	Mitotic count (10 HPF)	Mitotic count (10 HPF)	Ki-67 (%)
G1	< 2	<2	\leq
G2	2-10	2-20	3-20
G3	>10	>20	>20

The medical treatment of advanced well-moderately differentiated (G1/G2) neuroendocrine neoplasms has included somatostatin analogs, interferon and cytotoxic agents. The lack of effectiveness of conventional cytotoxic agents has prompted exploration of new targeted drugs exploiting phenotypical features of neuroendocrine neoplasms. Neuroendocrine neoplasms are characterized by being remarkably vascular and expressing several growth factors, including vascular endothelial growth factor (VEGF), platelet-derived growth factor (PDGF), insulin-like growth factor 1 (IGF-1), basic fibroblast growth factor (bFGF), and transforming growth factor (TGF)- α and - β . In addition, expression of several receptors of these growth factors and ligands has been described, including stem cell factor receptor (c-KIT), epidermal growth factor receptors (EGFR), VEGF receptors (VEGFR)-2 and 3, IGF receptors (IGF-R), and PDGF receptors (PDGFR). The (over)expression of some of these factors has been associated with poor prognosis and decreased progression-free survival (PFS), as well as with tumor growth, aggressiveness, and disease extent in patients with gastroenteropancreatic neuroendocrine neoplasms. Several targeted agents have been studied in the treatment of neuroendocrine neoplasms including antiangiogenic compounds (such as bevacizumab), inhibitors of multiple receptors with kinase activity (such as sunitinib), and inhibitors of intracellular downstream effector proteins such as the mammalian target of rapamycin (mTOR) everolimus. Three phase III studies with everolimus and sunitinib have demonstrated efficacy in G1/G2 neuroendocrine tumors of the gastroenteropancreatic system becoming new treatment options in the management of these patients (Raymond et al 2011; Yao et al 2011; Yao et al 2015). Everolimus has also demonstrated efficacy in G1/G2 lung neuroendocrine tumors (typical and atypical carcinoids), becoming the first drug that has demonstrated a significant increase in progression-free survival in this setting (Yao et al 2015).

For advanced high-grade neuroendocrine carcinomas (G3), regardless of the site of the primary tumor, combination chemotherapy using cisplatin-based regimens is recommended early (provided that the patient has adequate organ function and performance status). Responses are frequently seen, however impact in overall survival is limited and life expectancy of these patients is around 12-16 months. There is no established second-line therapy for G3 neuroendocrine carcinomas of the gastroenteropancreatic system.

Immune responses directed against tumors are one of the body's natural defense against the growth and proliferation of cancer cells. However, over time and under pressure from immune attack, cancers develop strategies to evade immune-mediated killing allowing them to develop unchecked. One such mechanism involves upregulation of surface proteins that deliver inhibitory signals to cytotoxic T cells. Programmed cell death ligand 1 (PD-L1) is one such protein, and is upregulated in a broad range of cancers with a high frequency, with up to 88% expression in some tumor types. In a number of these cancers, including lung (Mu et al, 2011), renal (Krambeck et al, 2007), pancreatic (Nomi et al, 2007; Loos et al, 2008), ovarian cancer (Hamanishi et al, 2007), and hematologic malignancies (Andorsky et al, 2011; Brusa et al, 2013) tumor cell expression of PD-L1 is associated with reduced survival and an unfavorable prognosis.

Programmed cell death ligand 1 is part of a complex system of receptors and ligands that are involved in controlling T-cell activation. PD-L1 acts at multiple sites in the body to help regulate normal immune responses and is used by tumors to help evade detection and elimination by the host immune system tumor response. In the lymph nodes, PD-L1 on antigen-presenting cells binds to PD-1 or CD80 on activated T cells and delivers an inhibitory signal to the T cell (Keir et al, 2008; Park et al, 2010). This results in reduced T-cell activation and fewer activated T cells in circulation.

Clinical Study Protocol
 Drug Substance DURVALUMAB/TREMELIMUMAB
 Study Number ESR 15-11561-61-DUNE
 EudraCT Nº: 2016-002858-20
 Edition Number: 5.0 dated on June 09th, 2021

In the tumor microenvironment, PD-L1 expressed on tumor cells binds to PD-1 and CD80 on activated T cells reaching the tumor. This delivers an inhibitory signal to those T cells, preventing them from killing target cancer cells and protecting the tumor from immune elimination (Zou and Chen, 2008).

Immune responses directed against tumors are one of the body's natural defenses against the growth and proliferation of cancer cells. T cells play a critical role in antitumor immunity and their infiltration and activity have been linked to improved prognosis in a number of cancers (Pagès et al, 2010; Suzuki et al, 2011). Immune evasion, primarily through suppression of T-cell activity, is now recognized as one of the hallmarks of cancer. Such evasion can occur via a range of mechanisms including production of suppressive cytokines such as IL-10, secretion of chemokines and growth factors that recruit and sustain suppressive regulatory T cells (Tregs) and inflammatory macrophages, and expression of inhibitory surface molecules such as B7-H1. Tumor types characterized as being responsive to immunotherapy-based approaches include melanoma, renal cell carcinoma (RCC), bladder cancer, and malignant mesothelioma (Bograd et al, 2011). Inhibition of CTLA-4 signaling is a validated approach to cancer therapy, as shown by the approval in 2011 of ipilimumab for the treatment of metastatic melanoma based on statistically significant and clinically meaningful improvement in OS (Robert et al, 2011).

In general, tumor response rates to anti-CTLA-4 therapy are low (~10%). However, in patients who respond, the responses are generally durable, lasting several months even in patients with aggressive tumors such as refractory metastatic melanoma. Because these agents work through activation of the immune system and not by directly targeting the tumor, responses can occur late and some patients may have perceived progression of their disease in advance of developing disease stabilization or a tumor response. In some cases, early growth of pre-existing lesions or the appearance of new lesions may have been due to immune-cell infiltration into the tumor and not due to proliferation and extension of neoplastic cells, *per se* (Wolchok et al, 2009). Overall, although the impact on conventionally-defined PFS can be small, durable response or stable disease seen in a proportion of patients can lead to significant prolongation of OS. The melanoma data with ipilimumab clearly demonstrate that a small proportion of patients with an objective response had significant prolongation of OS, supporting the development of this class of agents in other tumors. Although Phase 2 and Phase 3 studies of tremelimumab in metastatic melanoma did not meet the primary endpoints of response rate and OS, respectively, the data suggest activity of tremelimumab in melanoma (Ribas et al, 2013). In a large Phase 3 randomized study comparing tremelimumab with dacarbazine (DTIC)/temozolomide in patients with advanced melanoma, the reported median OS in the final analysis was 12.58 months for tremelimumab versus 10.71 months for DTIC/temozolomide (HR = 1.1416, p = 0.1272; Ribas et al, 2013).

